
**C.3. Participants.** Participants will be low-income mothers/infants (6mo at enrollment) *who are already receiving services from our HVP partner (Figure 6)*. Thus, study enrollment does not require that we recruit more families than our HVP partner is already enrolling. Mothers are enrolled in HVP services through outreach and screening pre-partum, in English or Spanish, at community health centers and hospitals. In order to be eligible mothers must meet a number of (but not all) risk criteria (e.g., low-income, housing instability). Enrolled mothers are matched to a home visitor (nurse) based on culture and language. **Recruitment.** Assessment workers (distinct from home visitors delivering services) who enroll families into services will introduce the study to mothers and obtain written consent. They will clarify with mothers that their refusal to participate in the study will not affect their receipt of any other services provided by the HVP. In our experience, families feel comfortable refusing if they are not willing to participate. Mothers/infants will be ineligible if they have any of the following conditions: eating disorders (e.g., bulimia nervosa), schizophrenia, and obesity-related syndrome (e.g., Prader Willi). Participants enrolled in a weight-loss program will be ineligible. Based on our pilot work, we expect to recruit 70% Hispanic/Latino, 13% African American, 8% White, 5% American Indian/Alaskan, 4% mixed race. **Retention.** We have learned a great deal about retention through our pilot work. For instance, most attrition from HVP services occurs in the first six months of services. Therefore, to maximize retention, mothers will be invited to participate in the study *after six months of home visits*. The unique relationship between home visitors and mothers facilitates subsequent retention, as many of these mothers are socially isolated and home visitors are important confidants and supports. We will use multiple strategies that are effective for high-risk populations to further retain the study sample: (1) gift cards of \$25 at each data collection, with all incentives paid after each assessment; (2) frequent contacts to maintain engagement and foster open communication; (3) quarterly newsletters to update subjects about study activities; (4) acknowledging birthdays and milestones; (5) reminder phone calls the day before the weekly visits and assessment sessions. **Randomization.** Randomization will be at the level of home visitors, who deliver the HVP (cluster randomization). Home visitors who serve mothers that are participating in the proposed study will be randomly assigned to deliver either HVP only or HVP+COPE. Potential concerns with randomizing by home visitors are feasibly addressed in this study. First, the likelihood of

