**Statistical Models Aims 1-3.** Our conceptual model includes three types of variables: Intervention arms (HVP vs. HVP+COPE) and covariates, mediators, and outcome variables. We will use multiple statistical procedures tied to the analytic objectives of each of our specific aims, including generalized linear modeling, path analysis and structural equation modeling (SEM) approaches. To control for potential cluster effect due to home visitors as families are nested with visitor, statistical models will be developed based on multilevel path analysis to test direct and indirect (or mediational) effects hypothesized in the model. The models involve two levels with mothers or children as Level-1 units and visitors as Level-2 units treated as a random effect. With multilevel path modeling approach, the covariance matrix to be analyzed can be properly decomposed into individual- and group-level covariances to account for the clustering effect due to visitor nesting effect of the data. The multilevel path model can involve all variables from the family level in the analysis. The model can also incorporate distal predictors and mediators from the visitor-level (Level-2) and outcomes from family-level (Level-1) data. The aims of the proposed study focus on the Level-1 units. Following Bentler-Weeks modeling notation, the path model can be expressed as:  $\eta = \beta\eta + \gamma\xi$ , with all exogenous (distal) variables defined as  $\xi$  and all endogenous (mediators and final outcomes) variables as  $\eta$ . The parameters in  $\beta$  and  $\gamma$  matrices can be specified according to the hypotheses of each Aim. Models to be developed are discussed in greater detail below for each Aim. Mplus software will be used model estimation and evaluation.

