**Aim 1 (maternal/infant outcomes).** Change in weight-related outcomes over the 2-year implementation is the primary outcome comparison. We will use multilevel regression models adjusting for clustering effect of home visitors to compare differences in the main outcomes across time by intervention arm. Regression model can be treated as a special case of path model without mediators. These regression models will include all participants, who have at least 2 measurements, regardless of when the measurements are taken, increasing the follow-up of study participants and statistical power. Specific measures relevant to Aim 1 are maternal and children weight-related measures. These models will allow the evaluation of intervention effects on, for example, child growth trajectory and activity, and mother BMI, metabolic, and behavior outcomes. Investigation of the main effects of COPE on outcomes will be conducted at each follow-up. Baseline outcome measures will be treated as covariates to control for potential

baseline differences. Effects of COPE will be evaluated first at each follow-up assessment point. Longitudinal analyses with all follow-up points (6 and 12 months) will then be conducted to examine profiles across time to investigate the effects of program conditions on trends of outcome measures.

**Aim 2 (maternal transmission).** To estimate the mediational effects of maternal transmission, multilevel path models will be developed and evaluated per our hypotheses. The model specification will be guided by our conceptual model treating Intervention program as the distal variables along with demographic variables to affect mother's weight, diet and behavior as mediators, which in turn may influence infants' outcome. While the intervention program will be at the Level-2 unit, all other variables included in the multilevel path models will be Level-1 variables obtained from mothers and children. Using breastfeeding and maternal diet on infants' weight trajectories as an example, the mediation mechanism of maternal transmission can be expressed by the process: COPE → breastfeeding \* maternal diet → weight. The path model will allow the test of both the direct effect of COPE on infant weight trajectory and its indirect effect on through breastfeeding and maternal diet.

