**Power Analysis Aims 1-3 (Figure 7).** A total of 30 home visitors will be recruited and randomized to HVP or HVP+COPE. With an average of 13 families served by each visitor, a total of 300 families will be invited to participate in the proposed study over 12 months. Based on our pilot work and existing HVP data, we expect a retention rate of 75% of families, which will result in a final sample of 200 mothers/infants. We have calculated power using G\*Power based on an effective sample of N=200 for the main weight related outcomes with the design of repeated measurement. All tests use a two-sided alpha level of .05. Our pilot study showed a small to medium effect size of .4 (Cohen's *d*) on our main outcome of children's weight velocity and smaller effect on energy intake at 6 months post-test. No previous study has investigated the long-term (12 months) delivery of in-home obesity prevention on 0-2yo children's growth trajectory, diet and activity. However, an in-home intervention compared to outpatient pediatric counseling resulted in a large effect size of 1.64 (Cohen's *d*) for changes in zBMI at 12 months, among obese 2-5yo children. To account for potential large clustering effect at the home visitor level, we assume the intraclass correlation (ICC) of .05 to .1 with inflation factors  $(1+(n-1)*ICC)$  of 1.4 to 1.8, respectively. After taking inflation factor into account, our proposed sample size of 200 will have enough power to detect medium effect sizes based on Cohen's *f* between .17 and .20. More comprehensive path model will be specified in each aim for model evaluation and hypothesis testing. We are aware of the sample size limitation and will be cautious in the number of variables and the size of the model involved. We used the hypothesis-testing framework of RMSEA to estimate power of model fitting in our study. With  $\alpha = .05$ , a null hypothesis RMSEA of .00 (almost exact fit for path model), an alternative hypothesis RMSEA of .08 (criterion of not acceptable models) and degrees of freedom (size of the model) ranging from 10 to 15, the range of statistical power for a sample size of 300 is between .83 and .93. We will have sufficient power to detect small to medium effect of a set of pre-selected parameters associated with mediators and outcomes with sample size of 200.

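### Sufficient power is claimed for small-to-medium mediator effects at N=200 with no clustering allowance shown, yet the COPE-to-mediator path rests on 30 visitors and falls short at d=.4

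*Combined protocol and SAP*

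**What the plan says.** All references are to the combined protocol and SAP.

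- **Unit of randomization.** C.3 states: "Randomization will be at the level of home visitors, who deliver the HVP (cluster randomization"). The power analysis in C.6 adds: "A total of 30 home visitors will be recruited and randomized to HVP or HVP+COPE".
- **Model.** C.6 (Statistical Models Aims 1-3) plans a two-level path model with visitors as a random effect. Under Aim 2 it states: "While the intervention program will be at the Level-2 unit, all other variables included in the multilevel path models will be Level-1 variables". Aim 3 uses a similar model.
- **Clustering in the power section.** C.6 assumes an ICC of .05 to .1, gives inflation factors of 1.4 to 1.8, and uses them to state that 200 families can detect Cohen's f of .17 to .20 on the main weight-related outcomes.
- **Power for the path models.** For an RMSEA test (null .00, alternative .08, 10 to 15 df), "the range of statistical power for a sample size of 300 is between .83 and .93". No inflation factor appears here.
- **Mediator claim.** "We will have sufficient power to detect small to medium effect of a set of pre-selected parameters associated with mediators and outcomes" is then asserted for 200 families, with a literature reference but no parameter value, ICC, number of visitors or power figure.
- **Test level.** "All tests use a two-sided alpha level of .05".
- **Effect size.** The pilot effect that the plan calls small to medium is d=.4, given for children's weight velocity. The plan reports a smaller effect on energy intake.

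**The concern.** All families of one visitor are in the same arm. The effect of COPE on a mediator can therefore be estimated only from differences between visitors, and its precision depends on 30 units as well as on the number of families. The plan recognises this when it inflates for the weight outcomes, but shows no such step for the path models.

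The figure that precedes the mediator claim cannot support it. Power of an overall-fit test is not power for an indirect effect, and it is quoted at 300 families when the planned final sample is 200.

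Two of the three specific aims concern mechanisms. If the real chance of detecting a true small-to-medium effect on a mediator is nearer one half to two thirds, a null result for breastfeeding, maternal diet or network support says much less than a reader of the power section would suppose.

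**Working it through.** **1. The plan's own figure.** Inputs from C.6: null RMSEA 0, alternative .08, df 10 to 15, alpha .05.

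Power = P[noncentral chi-square(df, λ) > 95th percentile of chi-square(df)], with λ = (N−1) × df × .08².

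| N | df | λ | critical value | power |
|---|---|---|---|---|
| 300 | 10 | 299 × 10 × .0064 = 19.14 | 18.31 | .873 |
| 300 | 15 | 299 × 15 × .0064 = 28.70 | 25.00 | .957 |
| 200 | 10 | 199 × 10 × .0064 = 12.74 | 18.31 | .672 |
| 200 | 15 | 199 × 15 × .0064 = 19.10 | 25.00 | .808 |

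The stated .83 to .93 does not reproduce at N=300. At the planned 200 the range is .67 to .81, with no deduction for clustering.

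**2. COPE-to-mediator path.** From the plan: 30 visitors, 200 families, ICC .05 to .10, two-sided alpha .05. Assumptions of this check: 15 visitors per arm (no ratio is stated), the same ICC range for mediators, mediator effect d=.4, no covariate adjustment.

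- Design effect: DEFF = 1 + (m−1) × ICC. With m = 200/30 = 6.67, DEFF = 1.28 (ICC .05) or 1.57 (ICC .10). The plan's 1.4 and 1.8 correspond to m = 9.
- SE(d) = √(4 × DEFF / N). Power is from the noncentral t with 30 − 2 = 28 df (critical value 2.048) and noncentrality d/SE.

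| Scenario, d=.4 | DEFF | SE | noncentrality | power |
|---|---|---|---|---|
| Independent families, N=200, 198 df | 1 | .141 | 2.83 | .80 |
| N=200, m=6.67, ICC .05 | 1.28 | .160 | 2.50 | .67 |
| N=200, m=6.67, ICC .10 | 1.57 | .177 | 2.26 | .59 |
| N=200, plan's factor 1.4 | 1.4 | .167 | 2.39 | .64 |
| N=200, plan's factor 1.8 | 1.8 | .190 | 2.11 | .53 |
| N=225 (75% of 300), ICC .05 | 1.325 | .153 | 2.61 | .71 |
| N=225, ICC .10 | 1.65 | .171 | 2.34 | .62 |

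Other effect sizes at N=200 and m=6.67, for ICC .05 and .10: d=.3 gives .44 and .37; d=.5 gives .85 and .78.

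The effect detectable with 80% power is d=.47 to .51 at m=6.67 and .49 to .55 with the plan's factors, against .40 under independence.

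**3. Indirect effect.** Under joint significance both legs must be significant, so power cannot exceed that of the first leg. Assume a mediator-outcome partial r of .20. With 200 families the second leg has power of about .82; it is a Level-1 path and is not limited by the number of visitors.

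- ICC .05: .674 × .819 = .55
- ICC .10: .588 × .819 = .48
- Independent families: .804 × .819 = .66

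A simulation of the joint test with 30 clusters and N=200 gave .476 at ICC .10, in agreement.

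**4. Baseline adjustment.** If a baseline measure of the mediator is a covariate with correlation ρ, SE² is multiplied by (1−ρ²). At d=.4, N=200, m=6.67, first-path power for ICC .10 to .05 is .71 to .79 at ρ=.5 and .86 to .92 at ρ=.7. The documents give no ρ.

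**The case against.** **Independence was not stated.** A reader might infer that the plan treated 200 to 300 families as independent for mediation. The text does not say so. The mediator sentence has no visible calculation, only a reference that cannot be checked here. What can be said is that no clustering allowance is shown.

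**The analysis is already multilevel.** This stands. C.6 makes visitors a random effect, places COPE at Level 2 with mediators and outcomes at Level 1 (a 2-1-1 structure), and cites work on multilevel mediation. The remark "The aims of the proposed study focus on the Level-1 units" describes where the variables lie and is not evidence that clustering was ignored. The fault is in the power statement.

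**The claim covers several parameters.** This also stands. At r=.20 the mediator-to-outcome path has about .82 at N=200, so for that parameter the claim can hold.

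**The inputs are borrowed.** The d=.4 belongs to weight velocity, and no ICC is given for mediators. Larger effects or a strongly correlated baseline mediator would restore power. That is why ranges are shown. The power section takes no credit for adjustment, and the smaller pilot effect on energy intake suggests that d=.4 is not plainly pessimistic.

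**Clustering is not the whole cause.** Even with independent families the indirect effect at d=.4 and r=.20 has only .66.

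**The fit-test mismatch at N=300 is conservative.** True: the stated range is below the recomputed one. The gap that matters is between 300 and 200. Other input values also come close to .83 to .93, so no explanation of that range should be inferred.

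**The plan admits a sample size limitation.** It does, but it does not quantify it, and it then asserts adequacy.

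**Conclusion.** The concern holds for the COPE-to-mediator path and for the indirect effects of COPE. At d=.4, ICC .05 to .10 and no adjustment, first-path power is .67 to .59, or .64 to .53 with the plan's own factors, instead of .80 under independence. The indirect effect is near one half if the partial r is .20. Using 225 families does not change the conclusion. These results assume that d=.4 and the stated ICC range apply to mediators and that visitors are split equally.

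The documents do not support the stronger reading that Aims 2 and 3 are underpowered throughout. Power is adequate or nearly so at d=.5 (.85 to .78 at 200/30 families per visitor), or with a strongly correlated baseline mediator. Separately, the fit-test figures are wrong as stated at N=300 and are given for the wrong sample size. This should be corrected. It does not affect the primary comparison, which is change in weight-related outcomes.

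**What to change.** In C.6, Power Analysis Aims 1-3:

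1. Correct the RMSEA power and give it at N=200 (.67 to .81 before clustering), identified as a test of overall fit.
2. State power for the COPE-to-mediator path and for the indirect effect with 30 visitors, N=200 and ICC .05 to .10. Label the mediator effect, the mediator-outcome association and any baseline correlation as assumptions.
3. Replace the sufficiency sentence with the effect that is detectable. For the first path at 80% power this is about d=.47 to .51 at 200/30 families per visitor, or .49 to .55 with the plan's factors.

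Keep the planned multilevel (2-1-1) model, and specify that indirect effects are reported with intervals that respect visitor clustering.

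The cost is a few recalculated figures and some wording; design and data collection are unchanged. The drawback is that the stated power becomes less favourable.

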complete rigorous training to learn the HVP curriculum and meet the requirements of Healthy Families America (the HVP model we are partnering with). They receive weekly supervision to review progress and address issues. (3) Home visitors delivering COPE receive a 2-day initial training and annual refresher courses from [name] and the onsite Health Families America dietitian and nutritionist, with scripted manuals and materials. [name] further reviews 25% of the sessions to monitor fidelity. (4) Weekly supervisions (home visitors) and bi-annual focus groups (families, home visitors, and Community Advisory Board) are conducted to review progress, dosage and timing of delivery, and provide the opportunity to resolve problems or issues encountered. (5) Intervention components are delivered in the home or at specified community-run settings (e.g., community garden), and meetings and supervisions with home visitors implementing different arms are held on separate days (at Antelope Valley Partners for Health) to minimize the risks of contamination. COPE supervision is embedded in the weekly supervision home visitors already receive to monitor their services. **Potential burden or weakening of HVP curriculum.** Potential concerns related to adding material to the existing HVP curriculum include (1) diluting or weakening HVPs' outcomes in other areas (e.g., parenting skills, maternal depression), and (2) increasing the burden on HVP staff and families. Our formative evaluation and pilot work indicate that these concerns are unfounded. COPE was designed collaboratively with our HVP partners (who are experienced in integrating new enhancement modules into the HVP curriculum) so that it would complement other program goals. For instance, home visitors report that COPE cooking and tasting activities are used to strengthen mother-child bonding and parenting skills (a standard HVP benchmark area). HVP directors also found no differences between HVP+COPE and HVP only families on HVPs' benchmark areas set by the Health Resources and Services Administration (i.e., maternal and newborn health; child abuse and neglect and emergency department visits; crime or domestic violence; family economic security; and coordination and referrals for other community resources and support). Concerns that COPE may overly burden families and lead to greater attrition was also not supported, as the dropout rate was considerably *lower* among mothers in the HVP+COPE group than among mothers in the HVP only group in our pilot study. These findings suggest that the addition of COPE does not weaken other HVPs' targeted outcomes, or overly burden families and home visitors. We will continue to monitor these outcomes throughout the implementation.

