2. **Social experiential activities (Table 5)** were selected in response to: our theoretical framework that emphasizes social network influences; our pilot work that highlights existing social network barriers to behavior change; and families’ desire to learn through hands-on, social activities. These activities are already built into the service infrastructure at Antelope Valley Partners for Health, are integrated across all key content areas of COPE, and will be promoted to participants in the intervention arm (but not to participants in the control arm) by their home visitor. Participation by study participants will be monitored and recorded by activity staff. One central purpose of the communal activities is to foster new, yet sustainable social and community connections that will provide increased healthy behavior role models and social support for mothers. This will be achieved through activities that provide a context for repeated social connection among consistent groups of COPE participants in their neighborhoods, and through activities designed to foster group learning, discussion, and shared experiences that are aligned with the individual didactic learning in home. These social activities are similar to those delivered as part of the *National Institute of Food and Agriculture’s Expanded Food and Nutrition Education Program*.

Table 5. Description of COPE experiential and communal activities	
Communal cooking	Advance meal preparation to promote home cooking using foods from WIC/food bank, and decrease reliance on fast-food. Gatherings are lead by [name] (Site Culinary Program Coordinator) and take place in the Wellness Homes operated by our partner (Resources & Environment section).
Community gardening	Mariposa master gardeners teach parents/children gardening techniques (planting, growing and harvesting fruits and vegetables). Gardens are located on Wellness Homes’ grounds. Families tend local gardens with other families.
Food management	Classes to improve food resource management practices such as purchasing, selecting, or otherwise obtaining; preparing; and storing foods to increase sustained availability of healthy foods throughout the month. This material is delivered in local grocery stores and markets.
Mobile food demos	Food demonstrations hosted in neighborhood farmers markets to provide convenient and accessible cooking and food preparation demonstrations using fresh products from local farmers markets.

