**Secondary Aim (Real-life economic analysis).** We will document the costs of adding COPE to HVP's services through cost logs and interviews with HVP directors. We will consider the costs of labor (the time home visitors spent in training and in administering COPE, times their wage rate) and of materials (training and intervention manuals for home visitors), and evaluate how these costs can be absorbed through the ongoing funding from the Affordable Care Act. We will calculate infants and mothers' weight, metabolic, and behavioral trajectories and how they differ by child gender, household structure, and other observables. These analyses will be conducted at two levels. First, we will calculate the cost-effectiveness of HVP+COPE (vs. HVP only) by comparing the cost of adding COPE per unit of improvements in weight, metabolic, or behavioral outcomes with the cost per unit of improvement in these outcomes vs. alternative obesity programs with similar aims (e.g., prevention delivered in outpatient settings). This will provide a measure of the effectiveness of COPE vs.

[figure not shown]

Figure 7. Required sample size by effect size

alternative interventions. We will rely on an extensive review of the literature to obtain estimates of costs and improvements associated with such alternative programs. Second, in the absence of long-term data, simulation models are often used to predict long-term outcomes and/or evaluate the cost-effectiveness of healthcare interventions. We have developed a simulation model to predict BMI trajectories and associated medical expenditures over the life cycle (e.g., ). The model utilizes data from the Medical Expenditure Panel Survey (MEPS) to model yearly changes in BMI and healthcare costs associated with each possible initial BMI state. The model was validated using data from the National Health and Nutrition Examination Survey (NHANES). This work shows that reducing by 10% the risks of overweight/obesity (BMI  $\geq$  85th percentile) in ages 2-18 is associated with reductions in direct medical costs between \$2,830 (men) and \$3,000 (women) in adulthood. Reducing obesity risks by 25% is associated with savings of \$5,860 and \$6,022 in adult men and women respectively. We will use this model to predict reductions associated with long-term BMI and medical care expenditures over the life cycle and compare these to costs associated with COPE.

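### The costing of COPE names only home-visitor time and manuals; without trainer time and communal-activity staff and supplies, its absolute cost is understated

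*Combined protocol and SAP*

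**What the plan says.** C.6, Secondary Aim (Real-life economic analysis), opens with a general commitment: "We will document the costs of adding COPE to HVP's services through cost logs and interviews with HVP directors". It then describes two categories. For labor: "We will consider the costs of labor (the time home visitors spent in training and in administering COPE, times their wage rate". For materials: "and of materials (training and intervention manuals for home visitors". No other staff group, supply or venue is named, and no costing perspective is stated.

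The resulting cost is used twice. The first use is a cost-effectiveness ratio, formed by "comparing the cost of adding COPE per unit of improvements in weight, metabolic, or behavioral outcomes" and set against other obesity programs, whose figures come from the literature: "We will rely on an extensive review of the literature to obtain estimates of costs and improvements associated with such alternative programs". The second sets the cost of COPE against simulated lifetime savings in medical expenditure.

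Elsewhere the protocol describes more inputs:

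- C.2, Treatment fidelity: COPE visitors "receive a 2-day initial training and annual refresher courses". These are given by a member of the study team with the onsite dietitian and nutritionist. A quarter of sessions is reviewed for fidelity. COPE supervision is said to sit inside the weekly supervision that visitors already have.
- C.4, social experiential activities and Table 5: communal cooking led by a site coordinator in the partner's Wellness Homes, gardening taught by master gardeners, food-management classes and mobile food demonstrations. The activities already exist at Antelope Valley Partners for Health, and home visitors promote them to the COPE arm but not to controls. On attendance: "Participation by study participants will be monitored and recorded by activity staff".

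**The concern.** The costed items and the delivered intervention do not match. Training is counted from the trainee's side only: visitors' hours enter, trainers' hours do not. The communal activities run across all of COPE's content areas and are meant to build the social ties that Aim 3 studies. Any benefit from them therefore enters the denominator of the cost-effectiveness ratio, while their staff and supplies are absent from the numerator.

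What is at stake is the credibility of the economic result. The protocol presents likely cost-effectiveness as part of the case for wider use (B.6, item h; B.9) and names nationwide deployment as its long-term goal (Section A). A cost that leaves out resources another site would have to supply is a weak basis for that case. Staff hours not logged as they occur are also hard to reconstruct later.

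**Working it through.** The documents give no cost, wage, hours or ratio for COPE, so there is no figure to reproduce. The check compares texts, then works out direction and illustrates size.

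**Step 1. Inputs used against inputs costed.**

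| Input to COPE | Where described | Named in the C.6 costing? |
|---|---|---|
| Visitor time in training and delivery | C.2, C.4 | Yes |
| Visitor manuals | C.2 | Yes |
| Trainer time, incl. dietitian and nutritionist | C.2 | No |
| Activity staff: cooking, gardening, classes, demonstrations | C.4, Table 5 | No |
| Food, garden and demonstration supplies | Implied by Table 5 | No |
| COPE supervision | C.2 | No, but described as absorbed in existing supervision |
| Review of 25% of sessions | C.2 | No, but its purpose is fidelity monitoring |

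Rows three to five are the gap. The last two are weaker and are taken up under the objection.

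**Step 2. Direction.** Let C be the counted cost, rC the omitted cost with r ≥ 0, and E the improvement, with E > 0. Then

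reported ratio / full ratio = (C/E) / [(C + rC)/E] = 1/(1 + r).

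This cannot exceed 1, so the absolute cost and the cost per unit of improvement can only be understated.

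**Step 3. Size under assumed r.**

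| r (assumption) | Reported ratio as share of full ratio |
|---|---|
| 0.10 | 91% |
| 0.25 | 80% |
| 0.50 | 67% |
| 1.00 | 50% |

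**Step 4. Trainer time alone, as an illustration.** From the documents: 30 visitors, 200 to 300 families, weekly visits, 12 months, a 2-day initial training, and training marked at months 6, 12, 24 and 36 in Table 7. Assumed: 1:1 allocation (15 visitors and 100 to 150 families in COPE), 52 sessions per family, 15 to 30 minutes of COPE content per session, three trainers, every training occasion lasting 2 days, and 8-hour days.

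- Trainer time, not counted: 3 × 2 × 4 = 24 days.
- Visitor training, counted: 15 × 2 × 4 = 120 days.
- Visitor delivery, counted, 100 families: 100 × 52 = 5,200 sessions, or 1,300 to 2,600 hours, or 162.5 to 325 days.
- Visitor delivery, counted, 150 families: 150 × 52 = 7,800 sessions, or 1,950 to 3,900 hours, or 243.75 to 487.5 days.
- Total counted: from 120 + 162.5 = 282.5 to 120 + 487.5 = 607.5 days.
- Trainer share of counted labor at equal wages: 24/607.5 = 4.0% to 24/282.5 = 8.5%.
- At twice the visitor wage: 48/607.5 = 7.9% to 48/282.5 = 17.0%.

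On these assumptions trainer time alone gives r of about 0.04 to 0.17 relative to counted labor, that is, a reported figure of about 96% to 85% of one including trainers. Activity staff and supplies come on top and cannot be approached this way, because the documents give no hours, frequency or attendance for them.

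**The case against.** **A reader might infer that the cost list is closed.** The text does not say so. It begins with cost logs and director interviews, says these costs will be considered, and nowhere says that others will not be. Interviews could bring further site costs to light. This stands: the fair statement is that the plan names two items and commits to no others, not that it excludes them.

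**A reader might add supervision and fidelity review to the omissions.** C.2 says COPE supervision is embedded in existing weekly supervision, so on the documents' account it adds no session. Holding the arms' meetings on separate days is a contamination control belonging to the trial. The 25% review would be about 1,300 sessions (25% of 5,200) to 1,950 (25% of 7,800), but its purpose is fidelity monitoring, so it is probably a research cost. Both objections stand, and neither item carries this point.

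**Activity cost depends on perspective.** The aim is the cost of adding COPE to existing programs, and the activities already run at one partner. On a strictly incremental view their marginal cost may be low. Controls are not said to be barred, so only the difference in use between arms counts. This stands in part. C.6 states no perspective that would justify a value of zero, extra attendance still uses staff time and food, and C.4 says nothing about such activities at the second partner, the Children's Bureau (also named in C.4).

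**A reader might conclude that the comparison with outpatient programs must favor COPE.** The documents do not show this. If the published programs also omit training and overhead, the two omissions may offset each other. Only the direction for COPE's own cost is certain.

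**Trainer time may be small.** Step 4 agrees, on its assumptions. It says nothing about activity staff.

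**Conclusion.** The concern holds in limited form. C.6 names home-visitor time and manuals as the cost of COPE and does not commit to costing trainer time or the staff and supplies of communal activities that belong to COPE and are promoted only to that arm. Applied as written, it understates the absolute cost of COPE and its cost per unit of improvement. The direction follows from the arithmetic, given a positive effect and some added cost for the omitted items. The size is unknown. The 91% to 50% range rests wholly on assumed values of r, and the 4.0% to 17.0% for trainers on assumed hours and wages.

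Trainer time, including the dietitian and nutritionist, is the firmest item because it is plainly added by COPE. Activity cost is less certain and turns on the perspective chosen. The comparison with simulated savings inherits the understatement on its cost side; the comparison with literature programs may or may not. Only the secondary aim is affected. The primary outcome, the sample size and Aims 1 to 3 are untouched.

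**What to change.** Amend C.6, Secondary Aim, as follows:

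1. State the costing perspective, and justify any input valued at zero.
2. Add to the cost logs trainer and dietitian/nutritionist time (preparation and delivery) and the incremental staff time and supplies for the Table 5 activities.
3. Allocate activity cost by the participation that activity staff already record, counting the difference in use between arms.
4. Report research-only cost, such as the 25% fidelity review, on a separate line outside the delivery cost.
5. Treat supervision as zero added cost only if the logs confirm that COPE takes no extra supervision time.
6. List which cost categories each literature comparator includes, and compare on matched categories where possible.
7. Add a sensitivity scenario for a site that lacks the activity infrastructure.

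The price is a few more lines in a log that is already planned, and probably a less favorable stated cost for COPE. No new participant data are needed. The lines should be in place before training and activities are logged.
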